4.1.2 Comparative Drug(s)

Not applicable.

4.2 Packaging and Labeling

The study drug used in this study is the marketed commercial product, Cresemba® for injection or investigational study drug for oral dosing. The study drug is prepared, packaged and labeled under the responsibility of qualified staff at Astellas Pharma Global Development (APGD)-Astellas US Technologies (AUST) or sponsor's designee in accordance with APGD-AUST or sponsor's designee Standard Operating Procedures (SOPs), Good Manufacturing Practice (GMP) guidelines, International Council for Harmonisation of technical requirements for registration of pharmaceuticals for human use (ICH) Good Clinical Practice (GCP) guidelines and applicable local laws/regulations.

In addition to the commercial labeling, the intravenous study drug will bear a protocol label conforming to regulatory guidelines, GMP and local laws and regulations that identifies the contents as investigational drug. The oral study drug will only bear a protocol label conforming to regulatory guidelines, GMP and local laws and regulations that identifies the contents as investigational drug.

4.3 Study Drug Handling

Current ICH GCP Guidelines require the investigator to ensure that study drug deliveries from the sponsor are received by the investigator/or designee and that:

- Such deliveries are recorded,
- Study drug is handled and stored according to labeled storage conditions,
- Study drug with appropriate expiry/retest and is only dispensed to study subjects in accordance with the protocol, and
- Any unused study drug is returned to the sponsor.

Study drug inventory and accountability records will be kept by the investigator designee. Study drug accountability throughout the study must be documented and reconciled. The following guidelines are therefore pertinent:

- The investigator designee agrees not to supply study drugs to any persons, except the eligible subjects in this study, in accordance with the protocol.

- The investigator designee will keep the study drugs in a pharmacy or other locked and secure storage facility under controlled storage conditions, accessible only to those authorized by the investigator to dispense these study drugs.
- A study drug inventory will be maintained by investigator designee. The inventory will include details of material received and a clear record of when they were dispensed and to which subject.
- At the conclusion or termination of this study, the investigator designee agrees to conduct a final drug supply inventory and to record the results of this inventory on the Drug Accountability Record. It must be possible to reconcile delivery records with those of used and/or returned study drug. Any discrepancies must be accounted for and documented. Appropriate forms of deliveries and returns must be signed by the site staff delegated this responsibility.
- The site staff must return study drug to the sponsor or designee at the end of the study or upon expiration unless otherwise approved by the sponsor.

4.4 Blinding

This section is not applicable as this is an open-label study.

4.5 Assignment and Allocation

All subject numbers will be assigned using the Interactive Response Technology (IRT) starting at screening. All subjects will have a unique, 10-digit subject number. The first 5 digits of this number will be the investigator's research number. The second 5 digits assigned will represent the subject's accession number. This will be the number that identifies a subject during the course of the study.

Only subjects who meet all inclusion criteria and exhibit none of the exclusion criteria will be enrolled into the study through IRT. Specific procedures related to the IRT are contained in the study procedures manual.

5 TREATMENTS AND EVALUATION

5.1 Dosing and Administration of Study Drug(s) and Other Medication(s)

5.1.1 Dose/Dose Regimen and Administration Period

The isavuconazonium sulfate will be administered as an intravenous infusion or as oral capsule(s) per the investigator's discretion. The 1-hour (\pm 10 minutes) intravenous infusion will be administered through an in-line filter. The start and stop times of the infusion must be clearly documented. Oral administration is only for subjects 6 to $<$ 18 years of age and with a body weight of at least 12 kg. The investigator may determine the appropriate route of administration for the subject in the context of the relevant age range. The route of administration can be interchangeable from intravenous to oral (6 to $<$ 18 years of age with a body weight of at least 12 kg) or oral (6 to $<$ 18 years of age and with a body weight of at least 12 kg) to intravenous during the loading dose period and throughout the treatment

period, the mg:mg is equivalent in both routes. The details of dose and route of administration will be captured in the electronic case report form (eCRF).

Treatment will be administered until the subject has a successful outcome as judged by the investigator or for a maximum duration of 84 days (IA) or 180 days (IM), whichever occurs first. Table 4 provides guidance to the investigator outlining the elements collectively informing a successful outcome. The investigator is encouraged to have clinical resolution of symptoms and associated mycological and/or radiologic data supporting the assessment of successful outcome.

Table 4 Investigator Guidance for Successful Outcome

	Clinical Response	Mycological Response	Radiological Response
Success	
Resolution of all attributable clinical symptoms and physical findingsPartial resolution of attributable clinical symptoms and physical findings	
EradicationPresumed Eradication	
Improvement from screeningNo signs on radiological images at screening (only for proven IFI based on other investigations)

IFI: invasive fungal infection

Intravenous Dosing:

Subjects weighing ≤ 37 kg:

- Loading regimen of 10.0 mg/kg isavuconazonium sulfate infusions every 8 hours (± 2) for 6 doses (days 1 and 2)
- Maintenance dose of 10.0 mg/kg isavuconazonium sulfate administered once daily starting 12 to 24 hours after the last loading dose

The maximum loading and daily maintenance doses to be administered to any subject are 372 mg per individual dose.

Subjects weighing > 37 kg:

- Loading regimen of 372 mg isavuconazonium sulfate infusions (1 vial) every 8 hours (± 2) for 6 doses (days 1 and 2)
- Maintenance dose of 372 mg isavuconazonium sulfate (1 vial) administered once daily starting 12 to 24 hours after the last loading dose

The maximum loading and daily maintenance doses to be administered to any subject are 372 mg per individual dose.

The maximum treatment is 84 days for IA subjects and 180 days for IM subjects, whichever occurs first.

Subjects will receive isavuconazonium sulfate as an intravenous infusion. The first maintenance dose should start 12 to 24 hours after the administration of the last loading dose. Subsequent maintenance doses will be administered once daily (24 hours \pm 2 hours from the previous maintenance dose).

Oral Dosing (for subjects 6 to < 18 years of age with a body weight of at least 12 kg):

Subjects will receive an oral loading regimen of isavuconazonium sulfate in a capsule form given every 8 hours (\pm 2 hours) on days 1 and 2 (a total of 6 doses), followed by once-daily oral maintenance dosing. The first maintenance dose should start 12 to 24 hours after the administration of the last loading dose, with subsequent maintenance doses to be administered once daily, 24 hours (\pm 2 hours) from the previous maintenance dose. Subjects who are discharged from the hospital with oral capsules for at-home administration must return weekly to receive new oral dosing supplies. Return visits should coincide with days when study-related assessments are required. Subjects who begin oral administration are to complete the oral dosing acceptability assessment after ingesting their first oral dose.

The daily dose is based on body weight and is intended to deliver a dose approximately equal to 10 mg/kg. The oral and intravenous formulations are equivalent on a mg:mg basis. The lower limit for oral dosing is 6 years of age and with a body weight of at least 12 kg.

Subjects will receive isavuconazonium sulfate as an oral capsule (the number of capsules will correspond to their weight; see Table 5).

Table 5 Oral Dosing Regimen by Body Weight

Body weight (kg)	Loading (Day 1 and Day 2)/Total Daily Isavuconazonium Sulfate Dose (mg)	Maintenance (up to 84 days [IA] or 180 days [IM])/Total Daily Isavuconazonium Sulfate Dose (mg)
12 to < 18	3 \times 2 capsules/447 mg	1 \times 2 capsules/149 mg
18 to < 25	3 \times 3 capsules/670.5 mg	1 \times 3 capsules/223.5 mg
25 to < 32	3 \times 4 capsules/894 mg	1 \times 4 capsules/298 mg
\geq 32	3 \times 5 capsules/1117.5 mg	1 \times 5 capsules/372.5 mg

Increase or Reduction in Dose of the Study Drug(s)

The mg/kg dose is to be consistent throughout study conduct. Dose increase or reductions to the study drug on a mg/kg basis are not allowed. However, if a subject has substantial weight changes, the number of capsules for oral dosing should be reassessed per Table 5.

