End of Treatment (EOT)	The date the last dose of study drug was taken by the enrolled subject. In this study, the end of treatment is a maximum of 84 days for invasive aspergillosis subjects or 180 days for invasive mucormycosis subjects.
Endpoint	Variable that pertains to the efficacy or safety evaluations of a trial.
Enroll	To register or enter a subject into a clinical trial. Note: Once a subject has received the study drug, the clinical trial protocol applies to the subject.
Evaluable Subject	A subject who has received at least one dose of study drug.
Intervention	The drug, device, therapy or process under investigation in a clinical study that is believed to have an effect on outcomes of interest in a study. (e.g., health-related quality of life, efficacy, safety and pharmacoeconomics).
Screen failure	Potential subject who did not meet 1 or more criteria required for participation in a trial.
Screening	A process of active consideration of potential subjects for enrollment in a trial.
Screening period	Period of time before entering the investigational period, usually from the time when a subject signs the consent until just before the test drug is given to a subject.
Study period	Period of time from the first site initiation date to the last site completing the study.
Variable	Any entity that varies; any attribute, phenomenon or event that can have different qualitative or quantitative values.

IV. SYNOPSIS

Date and Version # of Protocol Synopsis:	05 Sep 2019 / Version 4.0
Sponsor: Astellas Pharma Global Development Inc. (APGD)	Protocol Number: 9766-CL-0107
Name of Study Drug: Isavuconazonium sulfate	Phase of Development: 2
Title of Study: A Phase 2, Open-Label, Non-Comparative, Multicenter Study to Evaluate the Safety and Tolerability, Efficacy and Pharmacokinetics of Isavuconazonium Sulfate for the Treatment of Invasive Aspergillosis (IA) or Invasive Mucormycosis (IM) in Pediatric Subjects	
Planned Study Period: From 1Q2019 to 1Q2021	
Study Objective(s): Safety Objective To evaluate the safety and tolerability of isavuconazonium sulfate in pediatric subjects Efficacy Objective To assess the efficacy of isavuconazonium sulfate for the treatment of invasive aspergillosis (IA) or invasive mucormycosis (IM) in pediatric subjects Pharmacokinetic Objective To evaluate the pharmacokinetics of isavuconazole by monitoring the plasma concentrations in pediatric subjects during treatment with isavuconazonium sulfate	

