2. Follow-up is to be completed 30 (\pm 7) and 60 days (\pm 7) post-last dose from day 84 or EOT for IA subjects, and may be performed via telephone at the discretion of the investigator.
3. Diagnosis must be completed within 10 days of first dose.
4. Height is to be collected at baseline only. Weight is to be taken at baseline and day 84 or EOT.
5. Vital signs are to be measured within 1 hour prior to and approximately 1 hour after the end of each infusion. No additional vital signs are needed on dosing days for oral administration.
6. 12-lead ECG will be performed prior to study drug administration on each scheduled day.
7. Record assessments that are performed during the study to document response to antifungal therapy (e.g., serum galactomannan, radiology, mycological tests, changes in clinical signs and symptoms and any surgical procedure).
8. Pharmacokinetic trough samples should ideally be drawn immediately prior to the next dose of study drug, but must be taken no earlier than 1 hour prior to the next dose on days 7, 14, 21, 42 and 84 or EOT.
9. For both intravenous and oral dosing: 24-hour pharmacokinetic samples will be obtained on any one day between day 14 and day 42, while the subject is still receiving study drug, for subjects who consent to participation in the 24-hour pharmacokinetic assessment. The intravenous pharmacokinetic samples will be collected as follows: within 1 hour prior to the start of the intravenous isavuconazonium sulfate infusion. This sample will be the same as the trough sample prior to dose, if it coincides with scheduled days 14, 21 or 42, and immediately after the completion of the intravenous infusion (no more than 5 minutes after); and within 4 to 10 hours after the start of the intravenous infusion and within 16 to 24 hours after the start of the intravenous infusion (must be obtained before the start of the next infusion).
The oral pharmacokinetic samples will be collected as follows: within 1 hour of the next oral dose (this sample will be the same as the trough sample prior to dose, if it coincides with scheduled days 14, 21 or 42); 1 hour post dose (\pm 10 minutes); 3 hours post dose (\pm 10 minutes); 4 hours post dose (\pm 10 minutes); within 6 to 8 hours (\pm 30 minutes) of study drug administration; and 24 hours (within 1 hour before next study drug administration) after study drug administration.
10. Clinical (safety) laboratory samples will be assessed by the local laboratory.

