- 10 mg/kg isavuconazonium sulfate for subjects weighing \leq 37 kg (the maximum loading and daily maintenance doses to be administered to any subject are 372 mg)
OR
- 372 mg isavuconazonium sulfate for subjects weighing $>$ 37 kg.

NOTE: The oral administration is only available for pediatric subjects 6 years and older due to the difficulty in swallowing the oral capsule.

Due to similarity in exposures between intravenous and oral in pediatric subjects, the route of administration can be switched from intravenous to oral and oral to intravenous, as needed. Currently, interchangeability of administration is permitted in adults in approved product labeling (US Package Insert). Isavuconazonium sulfate oral capsules can be administered with or without food.

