5.4 Safety Assessment

5.4.1 Vital Signs

Vital signs (temperature, pulse rate and blood pressure) are to be measured within 1 hour before the start and approximately 1 hour after the end of each infusion on dosing days. No additional vital signs are needed on dosing days for oral administration. Temperature to be taken as per institution's policy based on age of subject. Vital signs will be collected as shown in the schedule of assessments [Table 1 and Table 2]. When vital signs are scheduled for the same time as a blood sample, the vital signs will be taken before the blood sample.

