5.4.3 Physical Examination

Subjects will be examined by a medically qualified person at the times specified in [Table 1 and Table 2 Schedule of Assessments].

A complete physical examination consisting of an examination of general appearance, eyes, nose, throat, neck (including thyroid), lymph nodes, chest, lungs, cardiovascular, abdomen, skin, extremities, musculoskeletal and neurological system including mental status is to be conducted. A symptom-directed physical exam may be performed during subsequent visits, if necessary.

Height will be measured at screening only. Weight will be measured at screening, day 84 or EOT (IA and IM subjects) and/or day 180/EOT (IM subjects).

The screening physical examination also includes significant, ongoing medical conditions. Any changes between screening and day 1 are to be captured in the medical history.

Any abnormal finding(s) at screening must not be exclusionary per the eligibility criteria if a subject is to be enrolled in the study. Post initial study drug dosing, new abnormal findings or a worsening of an ongoing abnormal condition must be recorded as an AE.

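### Capsule counts are to be reassessed after weight change, but the schedule weighs IA subjects only at screening and at the end of treatment, and IM subjects only once in between

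*Protocol*

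**What the plan says.** Section 5.1.1 states "The mg/kg dose is to be consistent throughout study conduct" and rules out increases or reductions on a mg/kg basis. It then allows one adjustment: "if a subject has substantial weight changes, the number of capsules for oral dosing should be reassessed per Table 5". Table 5 has four bands, from two capsules at 12 to <18 kg to five capsules at 32 kg and above. Intravenous dosing at 37 kg or less is given as "Maintenance dose of 10.0 mg/kg isavuconazonium sulfate administered once daily starting 12 to 24 hours after the last loading dose", with no date for the weight. Section 2.2.2 adds that "the route of administration can be switched from intravenous to oral and oral to intravenous, as needed".

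On weighing, footnote 4 of Table 1 says "Weight is to be taken at baseline and day 84 or EOT". Section 5.4.3 gives the same times and adds day 180 or EOT for IM subjects. Table 2 has a weight entry only in its day 180/EOT column. The key terms define EOT as "The date the last dose of study drug was taken by the enrolled subject".

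SAP Section 6.3 summarises average daily mg/kg doses for loading and maintenance, intravenous and oral, without naming the weight used as denominator.

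**The concern.** The dosing rule depends on knowing that a child's weight has changed during treatment, and the schedule does not collect that information while it could still be used. A site that follows the schedule exactly doses on the screening weight for up to 84 days (IA), or until day 84 and then on that weight up to day 180 (IM). The delivered mg/kg can then drift away from the constant value that Section 5.1.1 asks for. The children affected are those whose dose depends on weight: below about 32 kg for capsules and up to 37 kg for infusions, plus heavier children whose weight falls into those ranges. The mg/kg exposure summary inherits the problem, because an outdated denominator would hide the drift.

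**Working it through.** **1. Schedule against rule.**
- IA, full course: weights at screening (day -5 to day 1) and at day 84 ± 7 or EOT. The earliest second weight is 84 - 7 = day 77, when at most about a week of dosing remains.
- IA, early stop: the second weight belongs to EOT, which is defined by the last dose.
- IM: screening, day 84, then day 180 or EOT. Only the day 84 weight can still change dosing. The remaining 180 - 84 = 96 days have no further weight until the end, although Table 2 has visits at days 85, 115 and 145.
- Vital signs (Section 5.4.1) cover temperature, pulse rate and blood pressure, so they do not fill the gap.

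**2. Table 5 reproduced.** Maintenance mg = capsules × 74.5; loading = three times that per day.

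| Weight (kg) | Capsules | Maintenance / loading (mg) | mg/kg at lower edge | mg/kg at upper edge |
|---|---|---|---|---|
| 12 to <18 | 2 | 149 / 447 | 149/12 = 12.4 | 149/18 = 8.3 |
| 18 to <25 | 3 | 223.5 / 670.5 | 223.5/18 = 12.4 | 223.5/25 = 8.9 |
| 25 to <32 | 4 | 298 / 894 | 298/25 = 11.9 | 298/32 = 9.3 |
| ≥32 (shown to 37) | 5 | 372.5 / 1117.5 | 372.5/32 = 11.6 | 372.5/37 = 10.1 |

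All totals agree with the protocol. At the correct weight, the oral dose up to 37 kg lies between 8.3 and 12.4 mg/kg.

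**3. Size of one band.** Down: 5 to 4 capsules is -20%, 4 to 3 is -25%, 3 to 2 is -33%. Up: +50% (2 to 3), +33% (3 to 4), +25% (4 to 5).

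**4. Drift if the weight is not updated.** The documents give no weight-change data, so a 10% loss is an assumption.
- A 26 kg child falls to 23.4 kg. Oral on the old weight: 298/23.4 = 12.7 mg/kg. Re-banded: 223.5/23.4 = 9.6 mg/kg.
- The same child on infusion: 260/23.4 = 11.1 mg/kg on the old weight, against 234/23.4 = 10.0.
- Worst oral case, 18 kg falling to 16.2 kg on three capsules: 223.5/16.2 = 13.8 mg/kg.

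**5. Share of weights that change band after a 10% loss.** A weight w moves down when w ≥ edge and 0.9w < edge, so the affected width is edge/0.9 - edge.
- 18 kg: 2.00; 25 kg: 2.78; 32 kg: 3.56; total 8.33 kg.
- Evenly spread over 12 to 37 kg: 8.33/25 = 33%.
- Evenly spread over 12 to 60 kg: 8.33/48 = 17%.
- For a 5% loss the total is 3.95 kg, giving 16% and 8%.

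The answer halves when heavier adolescents are included, because everyone from 32 kg up receives five capsules. The documents give no weight distribution to choose between the ranges.

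**The case against.** **Sites will weigh children anyway.** Infusion outpatients attend daily and capsule subjects weekly (Section 5.1.3), and nothing forbids extra weighing. This is fair, and it probably limits the practical harm. But a routine weight is not a study requirement, so the rule would rest on data the protocol does not ask for. Section 4.1.1 also points to a package insert or pharmacy manual for dosage preparation. These are not among the documents, and a weighing rule there cannot be excluded.

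**The intravenous case is covered.** The sentence on a consistent mg/kg dose is not limited to capsules and can be read as making the infusion dose follow weight. That reading is reasonable and largely stands. It still needs a weight, and none is scheduled.

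**The exposure effect is modest.** With linear elimination and a clearance exponent of 0.75 (Section 2.2.2), an unchanged mg dose after a 10% loss raises AUC by 1/0.9^0.75 = 1.08, about 8%. The lower target of 60 mg·h/L and the lowest high-dose value of 233 are almost fourfold apart, and the adult analysis found no exposure threshold for response. This stands. It argues for a moderate rating, not for leaving a dosing rule without its input.

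**A threshold leaves much of the drift in place.** Also correct. With a 10% threshold, a child going from 33 to 31.35 kg (5% loss) would stay on five capsules at 372.5/31.35 = 11.9 mg/kg, which is within Table 5's own range. Drift of up to 1/0.9 - 1 = 11% would remain uncorrected, and oral doses just under 13.8 mg/kg would still be possible. The threshold is therefore a choice for the sponsor, with that cost stated.

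**Conclusion.** The concern holds, and should be fixed. As scheduled, the reassessment rule in Section 5.1.1 cannot operate for IA subjects before treatment is ending, and can operate once for IM subjects. One band is worth 20% to 50% of the dose. The frequency of such crossings is unknown; the 17% and 33% figures are illustrations that assume evenly spread weights and a 10% loss. The effect is confined to dosing accuracy and the mg/kg exposure summary. The mortality endpoint is untouched, and no formal sample size calculation was made.

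A reader might infer more, and the documents do not support it:
- *That deviation code PD3 (incorrect dose) becomes undecidable.* Two sites could dose the same child differently within the discretion of Section 5.1.1, but then neither has deviated. Section 8.3 also has the sponsor assess deviations with the investigator.
- *That the population PK analysis will be biased by an outdated weight.* That would require it to use the screening weight. Its details are in a separate analysis plan that is not available here.
- *That the undefined word substantial, or the unstated weight for infusions and route switches, is an error in itself.* These are mostly missing detail, worth settling in the same amendment.

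**What to change.** 1. Add body weight to Table 1 at the weekly treatment visits already planned, to Table 2 at days 115 and 145, and at any route switch; align footnote 4 and Section 5.4.3.
2. In Section 5.1.1, state that the most recent scheduled weight sets the capsule count (Table 5) and the infusion dose (10 mg/kg at 37 kg or less), including after a switch.
3. Replace the word substantial with a stated percentage change from the weight used for the current dose. The sponsor should choose it knowing the residual: a 10% threshold tolerates up to about 11% drift, a 5% threshold about 5% (1/0.95 - 1), with more frequent re-dosing.
4. In SAP Section 6.3, compute mg/kg from the latest weight on or before each dose.

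The cost is one non-invasive measurement at visits that already take place, an eCRF field and a few sentences of text. The downside is some extra dose changes in children near a band edge, which the threshold limits.
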